**Objective:**

The main objective of this research was to carry out an experimental study, triple blind, on the possible immunophysiological effects of a nutritional supplement (Synbiotic, Gasteel Plus®, Heel España S.A.U.), containing a mixture of probiotic strains, such as *Bifidobacterium lactis* CBP-001010, *Lactobacillus rhamnosus* CNCM I-4036, *Bifidobacterium longum* ES1, as well as prebiotic fructooligosaccharides, in both professional athletes and sedentary people.

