**Design:**

This investigation was a triple blinded, randomized, placebo-controlled pilot study designed to identify the possible differing effects of the synbiotic Gasteel Plus® supplementation between sedentary individuals and soccer players. Subjects were asked to maintain their regular lifestyle and the participants were prohibited from consuming probiotics, prebiotics or fermented products (yogurt or other foods) to avoid unnecessary interference during the experimental periods. Presenting injury or illness would result in exclusion from the study. All participants were also asked to provide written informed consent before participating in the study, which had been previously approved by the ethics committee of the Catholic University of Murcia (Spain) following current legislation (CE031810).

On two separate days, the "baseline-tests" and "final-tests" were conducted. All participants performed a series of tests, before which they had to fast. The order and schedule (8 am) of the tests was the same for the "final-test" and the same materials and procedures were used. A period of 30 consecutive days elapsed between the base-line and final tests, during which the participants had to ingest their supplement (synbiotic or placebo). Accelerometers were distributed one week prior to the baseline test and the week after the final test. Blood and saliva sampling were taken early in the morning and questionnaires were filled out on the two testing days. The treatment was carried out during the last fortnight of May 2019 and the first fortnight of June of the same year, coinciding with situations of possible physical and mental stress in both participant groups, being at the end of an examination period, as well as the end of the soccer season.

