### **Statistical Analysis Plan (SAP):**

Statistical analysis was performed with IBM statistics SPSS v20.0 software (SPSS Inc., Chicago IL, USA). To verify the normality of the data, the Shapiro-Wilk test was performed. The repeated two-way analysis of variance (ANOVA) was used, followed by Student's paired and unpaired t-tests to analyze the intervention effect. The values were expressed as mean  $\pm$  standard deviation (SD) and the significance level was considered when  $p<0,05$ .

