### Results:

Among the most important results we can observe:

the sedentary group administered with placebo obtained some significant differences with respect to baseline values ( $p<0,05$ ). A decrease in calories, metabolic rate and intensity level of physical activity are reflected. The synbiotic seems to prevent this situation by avoiding the mentioned decreases and even increasing the consumption of Kilocalorie (Kcal) in sedentary individuals although without significant differences. Results from the athlete group show no significant changes ( $p>0,05$ ) in those who consumed placebo, while those who followed the protocol with the intake of the synbiotic had significant improvements in sleep efficiency and latency, as well as increases in the consumption of Kcal and METS.

The baseline values are quite similar in the sedentary and athlete groups. Only in the athletes did the synbiotic intervention significantly improve ( $p<0,05$ ) the perceived general health as determined by the SF-36 questionnaire, but no differences were found in perceived sleep quality, state anxiety, and fatigue.

No significant differences were found in the perceived stress, trait anxiety, and depression between sedentary people and athletes at basal status (before intervention). The results show a decrease in the levels of perceived stress ( $p<0.01$ ) and anxiety ( $p<0.05$ ) only in the athlete group administered with the synbiotic. Also shows a decrease ( $p<0.05$ ) in perceived depression levels in both groups (sedentary and athlete) after the synbiotic treatment. Then, training only affected the behavior in response to the synbiotic intervention in stress and particularly in anxiety ( $p<0.05$ ) also when evaluating by the two way ANOVA test). These effects were not due to a placebo effect.

The results corresponding to blood concentrations of glucose, cholesterol, and triglycerides as measurements of metabolic profile. Firstly, individuals in both the sedentary and athlete groups presented lipid and glycaemic levels compatible with normal and healthy ranges. Thus, as expected the consumption of the synbiotic did not provoke an appreciable or significant effect

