It should be noted that both groups presented healthy baseline levels of the inflammatory and immune parameters analysed. No significant differences in the IL-1 $\beta$  concentrations were observed between the sedentary and athlete groups. However, a different behaviour ( $p<0.05$ ) between the two groups was found in response to the synbiotic intervention: while the synbiotic increased ( $p<0.05$ ) the systemic concentration of IL-1 $\beta$  in the sedentary group, it slightly decreased in the soccer player group.

No significant variations (except a potential placebo effect in the sedentary group) were found in the IL-10 concentration. There were also no significant differences in the levels of immunoglobulin A between groups, or as a consequence of the intervention.

A lower concentration without significant differences were found in the dopamine concentration of the soccer players group. However, training affected the response to the synbiotic intervention ( $p<0.05$ ), since it induced a significant increase ( $p<0.05$ ) in the dopamine concentration only in the athletes. This effect cannot be attributable to a potential placebo effect of the intervention. However, the decrease ( $p<0.05$ ) in epinephrine levels in the sedentary group administered with the synbiotic compared to their basal levels could potentially be attributed to a placebo effect of the intervention. In addition, there were also no significant changes in norepinephrine. Basal concentration of serotonin was, however, higher ( $p<0.05$ ) in the athlete group than in the sedentary group, but statistical differences with the synbiotic intervention were not observed.

Finally, the results corresponding to CRH showed a lower systemic concentration of CRH than sedentary volunteers. In addition, the behaviour of CRH secretion in response to the synbiotic intervention was also different ( $p<0.05$ ) between the athlete group and the sedentary group, decreasing significantly ( $p<0.05$ ) in the sedentary group with respect to their baseline levels (as also found with the placebo) and increasing slightly in the athlete group. The latter cannot be attributable to a placebo effect of the intervention. There were no significant differences in levels of cortisol and ACTH between groups or as a consequence of the intervention.

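### The Results attribute different responses in dopamine, perceived stress and anxiety to training, but training status was not randomised and the design cannot single it out as the modifier

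*Combined protocol and SAP*

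**What the plan says.** The Objective is to study the supplement "in both professional athletes and sedentary people". The Design section describes the trial thus: "This investigation was a triple blinded, randomized, placebo-controlled pilot study". The only thing allocated is the product: over 30 days "the participants had to ingest their supplement (synbiotic or placebo"). Training was not manipulated: "Subjects were asked to maintain their regular lifestyle". The Design adds that the treatment weeks coincided with possible stress in both groups, "being at the end of an examination period, as well as the end of the soccer season".

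On analysis, the SAP says: "The repeated two-way analysis of variance (ANOVA) was used, followed by Student's paired and unpaired t-tests to analyze the intervention effect". It does not name the two factors, and it mentions no matching, covariate or contrast that combines group, product and time.

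The Results then use causal wording twice. For the questionnaires: "training only affected the behavior in response to the synbiotic intervention in stress and particularly in anxiety". For dopamine: "training affected the response to the synbiotic intervention", on the ground that dopamine rose significantly in the athletes only. Neither sentence is qualified, and confounding is not mentioned as a limitation.

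**The concern.** Randomisation supports causal statements about what was randomised, which here is synbiotic against placebo. Professional soccer players and sedentary people differ in more than training. The Results themselves report higher baseline serotonin in the athletes (p<0.05) and describe their CRH as lower. Stress context may differ too, and perceived stress and anxiety are direct measures of it.

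The Design says that the study was meant to identify differing effects of the synbiotic in these two populations, so the two sentences bear on its stated purpose. A reader could take from them that training changes how a person responds to the product. The most that this design could show is that the response differed between these two groups.

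**Working it through.** The document gives no sample size, SD or effect size for these outcomes, so there is no stated figure to reproduce. The check is one of logic, with an illustration.

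**1. What each comparison estimates.** Let g_A and g_S be the 30-day changes that athletes and sedentary participants would show on placebo. Let e_A and e_S be the synbiotic-minus-placebo effects in the two groups.

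- Athletes against sedentary, synbiotic arm only: (e_A + g_A) − (e_S + g_S) = (e_A − e_S) + (g_A − g_S).
- Group by product by time: [(e_A + g_A) − g_A] − [(e_S + g_S) − g_S] = e_A − e_S.

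The first mixes a difference in synbiotic effect with a difference in background drift. The second removes the drift.

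**2. What neither comparison gives.** As a simple decomposition, write e_A − e_S = T + U, with T the part due to training and U the part due to every other difference between the populations. One contrast cannot separate two unknowns. Neither the placebo arm nor a larger sample changes that.

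**3. Which comparison was reported.** The SAP leaves its two factors unnamed. If time is one of them, only one place is left for group or product. No group-by-product-by-time result appears in the Results. The ANOVA p-value in the questionnaire sentence follows anxiety, and it is unclear whether it also covers stress.

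**4. Whether drift could differ by group.** The Results report significant falls in calories, metabolic rate and activity intensity in sedentary participants on placebo, but no significant change in athletes on placebo. CRH also fell in sedentary participants on placebo. These are not formal comparisons between groups, but they make g_A ≠ g_S plausible.

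**5. Illustration.** Assumptions: no synbiotic effect, no training effect, change-score SD of 1, two-sided α = 0.05, n per cell (four cells), and drift that differs between the groups by d SD. There were 20,000 simulated trials per setting. Both n and d are assumed, not taken from the document. The entries are the share of trials with p<0.05.

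| Comparison | d (SD) | n=6 | n=10 | n=15 |
|---|---|---|---|---|
| Time by group, synbiotic arm | 0 | 5% | 5% | 5% |
| Time by group, synbiotic arm | 0.5 | 13% | 18% | 26% |
| Time by group, synbiotic arm | 1.0 | 35% | 56% | 75% |
| Time by group by product | 0 to 1.0 | 5% | 5% | 5% |

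The unrounded values in the last row run from 4.8% to 5.3%. A normal approximation for the synbiotic-arm test gives 14%, 20% and 28% at d = 0.5, and 41%, 61% and 78% at d = 1.0, in reasonable agreement.

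**6. Precision of the three-way contrast.** Its standard error is √(4s²/n) = 2s/√n, with 4(n − 1) degrees of freedom. With s = 1, the 95% half-width is:

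- n=6: 2.086 × 2/√6 = 1.70 SD
- n=10: 2.028 × 2/√10 = 1.28 SD
- n=15: 2.003 × 2/√15 = 1.03 SD

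**The case against.** The best defence is the placebo arm. A stressor that acts on a whole group reaches synbiotic and placebo participants alike, so it does not by itself create a synbiotic-placebo difference. The Results also say that the stress, anxiety and dopamine findings were not placebo effects. This stands as far as it goes: the within-group comparisons of synbiotic with placebo are randomised and are not in question. But ruling out a placebo effect does not make training the explanation. Stress context remains one possible modifier among several.

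A reader might infer that the two groups certainly faced different stressors, so that training and stress context are completely inseparable. The document does not support that. The Design names an examination period and the end of the season but does not say which group had which, and some players may also have been students. The Results report no significant baseline difference in perceived stress, trait anxiety or depression. That does not establish equivalence or similar 30-day courses, but it counts against treating a stress imbalance as fact. The concern does not need one: unrandomised training status is enough.

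It is also fair to say that the causal wording is limited in scope. It covers dopamine, stress and anxiety. The IL-1β and CRH responses and the baseline serotonin difference are described as differences between groups, and the Design's aim is worded the same way.

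**Conclusion.** The concern holds for the two sentences on dopamine and on stress and anxiety. They make a causal claim about an unrandomised status, without adjustment, matching or a stated limitation. This follows from the design alone and does not depend on the simulation or on any view about who sat examinations.

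No size can be put on the error, since the part of a difference in response that is due to training is not identifiable here. The 13% to 75% in the illustration is a separate matter: it shows how often assumed drift differences of 0.5 to 1 SD would make a comparison confined to the synbiotic arm look significant when nothing is going on. It is not an estimate for this trial.

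It would go too far to conclude that training has no influence, that stress context produced the findings, or that the randomised supplement comparisons are invalid. The document shows none of these.

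**What to change.** 1. In both sentences, replace the statement about training with one saying that the change on synbiotic differed between soccer players and sedentary participants.
2. State that this is an association with group and cannot be attributed to training, because the groups were not randomised and may differ in other respects, possibly including stress context.
3. From data already collected, report the group-by-product-by-time contrast with its 95% confidence interval for dopamine, perceived stress and anxiety. Say that the synbiotic-placebo difference itself differed between groups only where this contrast supports it.

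Models that cross the supplement with baseline activity or baseline perceived stress are not required. Those variables are not randomised either, so they could not separate training from the other differences.

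The cost is two sentences, one limitation and one contrast for each of these outcomes, with no new participants. The conclusion becomes weaker, and in a pilot the interval will probably be wide.
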